2.4.4 Poolability Analysis

The distribution in AE-free rates across centers will be examined. The significance of differences in rates between centers will be initially tested using a Kruskal-Wallis test statistic, with an associated p-value of 0.15 or less considered evidence of center differences.

Additionally, a Cochran-Mantel-Haenszel test with continuity adjustment will be used to assess the poolability of data collected across the different centers. If evidence is found of center differences, then the reasons for the differences will be explored using Cox and logistic regression methods to determine if any baseline subject risk factors are explanatory.

3. PROTOCOL REQUIREMENTS

3.1 SUBJECT POPULATION

The investigator is responsible for screening all potential patients and selecting those who are appropriate for study inclusion. The subject selected for participation should be from the investigator's general patient population according to the inclusion and exclusion criteria described below.

3.1.1 Indications

The Plexa steroid-eluting, bipolar transvenous lead system is intended for use in the right ventricle of patients for whom implantable defibrillators are indicated. For this registry, the Plexa lead is utilized in conjunction with any US market released ICD or CRT-D device.

3.1.2 Contraindications

Do not use the Plexa lead system in patients with severe tricuspid valve disease or patients who have a mechanical tricuspid valve implanted. The Plexa steroid-eluting leads are contraindicated for patients who cannot tolerate a single systemic dose of up to 1.02 mg dexamethasone acetate (DXA).

3.1.3 Inclusion Criteria

To support the objectives of this investigation, the inclusion criteria at the time of subject enrollment for this registry include the following requirements:

- Successfully implanted with a BIOTRONIK ICD or CRT-D compatible system along with the Plexa lead no more than 30 days prior to consent[†]
- Able to understand the nature of the registry and provide informed consent
- Available for follow-up visits on a regular basis at the study site for the expected 5 years of follow-up
- Accepts BIOTRONIK Home Monitoring[®] concept
- Age greater than or equal to 18 years

3.1.4 Exclusion Criteria

To support the objectives of this investigation, the exclusion criteria at the time of subject enrollment include the following requirements:

- Enrolled in any investigational cardiac device trial
- Enrolled in BIOTRONIK's QP ExCELS lead study
- Planned cardiac surgical procedures or interventional measures within the next 6 months
- Expected to receive heart transplantation or ventricular assist device within 1 year
- Life expectancy of less than 1 year
- Patients reporting pregnancy at the time of enrollment

[†] Sponsor may approve a site specific waiver upon written request to allow enrollment prior to implant per institution's requirements.

3.2 REGISTRY PROCEDURES

Subjects will be enrolled no more than 30 days from implant of a BIOTRONIK ICD or CRT-D device and Plexa lead. BIOTRONIK Home Monitoring® should be activated in subjects who have a BIOTRONIK Home Monitoring® system. BIOTRONIK Home Monitoring® data can be utilized to assist in triage and diagnosis of lead-related adverse events between scheduled follow-ups. All subjects are required to be seen in-office once between the 24 and 36 month intervals and once at the 60 month interval. For all other visits, subjects may use BIOTRONIK Home Monitoring® follow-ups to meet the study visit schedule. Subjects without a BIOTRONIK Home Monitoring® system should be seen in-office for all intervals per the study visit schedule.

Registry Procedure Visits:

- Implant (collected retrospectively during enrollment)
- Enrollment
- Routine follow-up evaluations at 3 months post-implant, 6 months post-implant, and every 6 months thereafter for 5 years
- Interim follow-up information is only collected in support of AEs and is not required to be entered as a visit in the EDC
- System revision (if applicable)

Table 5 summarizes the visit assessment schedule.

Table 5: Registry Visit Assessment Schedule

	Implant ¹	Enrollment	Routine Follow-up Intervals ²	Interim Evaluation ³	System Revision
Informed consent		X			
Demographics and medical history ¹		X			
Implant information ¹	X ¹	X ¹			X ¹
Device evaluation	X		X	X	X
Adverse event assessment	X	X	X	X	X
Complete eCRFs	X	X	X	X	X

¹ Data may be collected retrospectively. Implant data is collected retrospectively at the enrollment visit. Implant information is also collected at system revisions regardless of the location of the procedure. Demographics and medical history information may also be collected retrospectively during the enrollment visit.

² 3, 6 months post-implant and every 6 months thereafter for 5 years post-implant. All subjects are required to be seen in-office once between the 24 and 36 month intervals and once at the 60 month interval. For all other visits, subjects may use BIOTRONIK Home Monitoring® follow-ups to meet the study visit schedule. Subjects without a BIOTRONIK Home Monitoring® system should be seen in-office for all intervals per the study visit schedule.

³ Interim follow-up information is only collected in support of AEs and is not required to be entered as a visit in the EDC.

3.2.1 Registry Pre-Screening

Prior to enrollment, the patient's medical history must be reviewed in order to ensure the patient is an appropriate candidate for the registry. In addition, all patients must satisfy the registry inclusion and exclusion criteria prior to enrollment, including having been implanted with a Plexa lead and BIOTRONIK ICD or CRT-D no more than 30 days before consent.

3.2.2 Plexa Lead Implant

Implant information is collected retrospectively during the enrollment visit. Implant details and device data will be collected retrospectively as follows:

- Implant information
 - Date of implant
 - Implantation site (right or left) and, if available, implant approach (e.g. subclavian, axillary, etc.)
- Information on implanted system (pulse generator and leads manufacturer / model, serial numbers, etc.)
- Electrical parameters of the Plexa lead (if available, at least one pacing threshold measurement for each lead at 0.4 ms pulse width)
- Any lead-related, pulse generator-related and procedure-related adverse events occurring during implant

3.2.3 Enrollment Visit

If the patient has been determined to be eligible for the registry, informed consent must be obtained from the patient prior to initiating any registry related data collection. The consent process, including discussion of the registry, should be documented in the patient's medical record. A subject with a successfully implanted Plexa lead is considered enrolled in the registry upon signing the Informed Consent Form. The visit at which informed consent is obtained is the enrollment visit and occurs no more than 30 days after the date of implant. The system the subject has at the time of signing the Informed Consent Form will be considered the study system. Prior implanted systems will not count as part of the study and AEs will only be collected from the time of the study system implant. Subject demographics are to be obtained at the enrollment visit; however, some information may be historical if it is not available with proper source documentation.

The following data collection and reporting procedures are performed at the enrollment visit:

1. Obtain informed consent
2. Collect subject demographics (date of birth, gender, etc.)
3. Collected medical history of subject, including device implant indications
4. Obtain data from the implant procedure as outlined in Section 3.2.2
5. Perform routine device interrogation:
 - Determine ICD lead mean R-wave sensing amplitude
 - Determine ICD lead pacing threshold at 0.4 ms pulse width
 - Determine the ICD lead pacing impedance
 - Determine the ICD lead shock impedance

- If Plexa DX ICD lead, determine atrial dipole mean P-wave amplitude
- Enable BIOTRONIK Home Monitoring® (if not already enabled)
- Enable RV automatic threshold management (ATM) or RV ventricular capture control (VCC)

6. Complete all required eCRFs

3.2.4 Routine Follow-ups

Subjects will undergo an assessment of their implanted system 3 months (\pm 30 days) post-implant, 6 months (\pm 45 days) post-implant, and every 6 months (\pm 45 days) thereafter for 5 years. All subjects are required to be seen in-office once between the 24 and 36 month intervals and once at the 60 month interval. For all other visits, subjects may use BIOTRONIK Home Monitoring® follow-ups to meet the study visit schedule. Subjects without a BIOTRONIK Home Monitoring® system should be seen in-office for all intervals per the study visit schedule. Figure 6 provides the visit schedule for a subject using BIOTRONIK Home Monitoring®.

Each site Principal Investigator (PI) will be trained to identify and schedule follow-ups to meet the required visit expectation. Additionally, the electronic data capture system (EDC) will provide assistance in identifying properly scheduled follow-ups according to this protocol.

The following data should be collected:

1. Perform routine device interrogation:
 - Determine ICD lead mean R-wave sensing amplitude
 - Determine ICD lead pacing threshold at 0.4 ms pulse width
 - Determine the ICD lead pacing impedance
 - Determine the ICD lead shock impedance
 - If Plexa DX ICD lead, determine atrial dipole mean P-wave amplitude
2. Determine if there have been any study defined adverse events (see Section 9)
3. Export and store the electronic device interrogation
4. Complete all appropriate eCRFs

The following data collection and reporting procedures are performed for a BIOTRONIK Home Monitoring® evaluation:

1. Check “Last message” date on Quick View page to ensure the visit occurred within the visit window
2. Review the data and save the Quick View page of the appropriate transmission
3. Determine if there have been any study defined adverse events (see Section 9)
4. Complete all appropriate eCRFs

3.2.4.1 Device Programming

If BIOTRONIK Home Monitoring® evaluations will be used for routine follow-up visits, atrial and / or ventricular capture control should be programmed to “ON” or “ATM,” and BIOTRONIK Home Monitoring® activated to allow collection and evaluation of pacing threshold data. If atrial and / or ventricular capture control is not programmed “ON” or “ATM,” the subject should be seen in-office for study visits. If the atrial and / or ventricular capture control is disabled automatically due to AF, high intrinsic rate, or other reason, the reason should be documented in the EDC system and if the reason is unable to be resolved, the subject should be seen in-office for study visits.

3.2.5 Interim Follow-ups

Interim follow-ups may occur anytime during the registry. Data collected during interim follow-ups should be the same as a routine in-office follow-up. Interim follow-up data is only collected in EDC in support of lead or system related AEs or system revisions and is not required to be entered as an interim follow-up in EDC. Other hospital or clinic visits that are unrelated to the device are not required to be collected.

3.2.6 System Revisions

For interim evaluations that involve a system revision (even if the Plexa lead is not directly affected), the following should be completed:

1. Collect implant information
 - Date of revision
 - Implant site (right or left) and if available implant approach (e.g. subclavian, axillary, etc.)
 - Implant location of pulse generator and implanted leads
 - Whenever possible, devices that are explanted should be returned to BIOTRONIK for analysis
2. Collect information on newly implanted system (pulse generator and leads manufacturer / model, serial numbers, etc.)
3. Record electrical parameters of the implanted leads (perform at least one pacing threshold measurement for each lead at 0.4 ms pulse width)
4. Record any lead-related, pulse generator-related and procedure-related adverse events during implant and complete the Adverse Event eCRF
5. Set programming parameters to best suit the needs of the subject
6. Complete System Revision eCRF, as applicable

If the Plexa lead is replaced with another Plexa lead attached to a US market released BIOTRONIK pulse generator, the subject may continue participation in the registry based on the original implant date and visit schedule. If the Plexa lead is explanted and the subject is not re-implanted or will not be re-implanted with a new Plexa lead attached to a US market released BIOTRONIK pulse generator, the subject will be withdrawn from the registry. See Section 10.2.3 for details on withdrawals due to lead or pulse generator extraction.

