2.4.3 Missing Data

All possible steps will be taken to minimize missing data in the registry. This includes but is not limited to monitoring of registry electronic case report forms (eCRFs) for completeness and supporting efforts to track and maintain contact with registry subjects during the follow-up period.

The reasons for any missing data in the registry should be documented. BIOTRONIK Home Monitoring[®] can provide daily automatic sensing values, pacing thresholds, shock impedance, and pacing impedance, depending on the device programming. When available, missing data will be imputed with BIOTRONIK Home Monitoring[®] values obtained from the day of a completed follow-up, target date of a missed follow-up, or the next closest day in the visit window.

For evaluation of primary endpoint1, only subjects who achieve 5 years of follow-up or have experienced an adverse event prior to 5 years will be included in the final evaluation of the associated hypotheses. The secondary endpoints 1 and 4 of other AEs at 5 years will be analyzed in a similar manner. There will be no imputation for these missing adverse event outcomes.

For purposes of the final report Kaplan-Meier survival analyses, all AE data on enrolled non-replaced subjects will be included with follow-up times censored at the time of exit or last completed study visit representing the time of the last known AE status.

Secondary endpoints 2 and 3, which include pacing thresholds, sensing, pacing impedance, and shock impedance measurements will be summarized by scheduled visit through the 5 years of registry follow-up

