4.2 ELECTRONIC CASE REPORT FORMS (eCRFs)

Original data will be collected at each study site and recorded into the EDC system, audited and monitored by BIOTRONIK, via completion of eCRFs. The investigator will be required to use an electronic signature to approve the content of the data reported in the eCRFs.

Information from electronically delivered source data (e.g. programmers) will be captured and stored in a validated environment until the end of the registry.

Subject follow-up is required for all subjects enrolled in this clinical registry. The required follow-up visit dates are based on Plexa lead implant date, and are to be used for the calculation of the dates of the routine follow-up schedule. The following eCRFs will be available in the EDC system:

- Informed Consent
- Enrollment
- Implant
- Lead Values (used for implant lead values and revision lead values)
- Follow-up (3 month \pm 30 days post-implant, 6 months \pm 45 days post-implant, and every 6 months \pm 45 days thereafter for 5 years)
- Adverse Event
- System Revision
- Study Termination
- Protocol Noncompliance

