9.2 ENDPOINT ANALYSIS

All protocol defined adverse events included in the primary and secondary endpoint analysis will be adjudicated by the Clinical Events Committee (CEC) (see Section 2.1, Section 6.2, and section 9.3). For each adverse event, the CEC will indicate whether the adverse event relatedness to the Plexa lead is: not related, related, possibly related, or unknown.

In evaluation of primary endpoint 1 and secondary endpoint 1 for the registry, the estimates of AE rates will be based on the number of subjects with at least one “related” AE as a proportion of total subjects. Subjects with a final adjudicated related AE classification of “possibly related”, “not related” or “unknown” will not have that individual event contribute to or be included in the evaluation of primary safety endpoint. The same rules will be used for purposes of Kaplan-Meier survival analyses, described in Section 2.4.2.

Secondary endpoint 4, which includes AEs that were excluded from primary safety endpoint 1 through 5 years post-implant, will also be summarized as AE rates along with their associated, exact 95% confidence intervals.

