APPENDIX A: DEFINITION OF TERMS

Abnormal defibrillation impedance – Defibrillation impedance is typically considered abnormal if a measurement is $< 25 \Omega$ or $> 150 \Omega$ (based on lead model and measurement range of the device). Includes high or low shock impedance when attempting to deliver a shock.

Abnormal pacing impedance – Pacing impedance is typically considered abnormal if a measurement is $< 200 \Omega$ or $> 3000 \Omega$ (based on lead model and measurement range of the device).

ACC / AHA – American College of Cardiology / American Heart Association

AE (Adverse Event) – An unwanted affect detected in participants either implant procedure related, lead related, or other. The term is used whether or not the effect can be attributed to the leads in the study. For the purposes of this study, the CEC will indicate whether the adverse event's relation to the Plexa lead is: related, possibly related, not related, or unknown.

Cardiac perforation associated with a lead – Penetration of the lead tip through the myocardium (including microperforation), clinically suspected and confirmed by chest X-ray, fluoroscopy, echocardiogram, intracardiac electrogram, or visual observation.

CFR – Code of Federal Regulations

Chronic threshold – Chronic threshold is defined as the pacing threshold determined at the subject's 3 month follow-up visit. If a 3 month follow-up visit is not completed, the chronic threshold is considered the first available threshold after the 3 month follow-up interval.

Clinical failure – Inability of the lead to correctly sense or pace in the heart, not attributable to a physiologic reason (e.g. new onset atrial fibrillation) or a mechanical malfunction of the lead or pulse generator that remains unresolved despite reprogramming and / or repositioning.

DF-1 – the international standard whereby leads and generators from different manufacturers are assured a basic fit [Reference ISO 5841-3:2013]

DF4 – the international standard for defibrillation lead connectors [Reference ISO 27186:2010]

Exit block – The failure of an intact pacing system to capture the heart because the stimulation threshold exceeds the output of the pacemaker.

Explantation – Surgical removal of a lead during the acute implant stage, whereby the lead has not been chronically implanted and can be easily removed by simple traction.

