Extracardiac stimulation – Clinical observation of inadvertent nerve / muscle stimulation other than cardiac muscle, such as the diaphragm or pectoral muscles..

Extraction of a lead – Surgical removal of a chronically implanted lead.

Failure to capture or intermittent capture – Intermittent or complete failure to achieve cardiac stimulation at programmed output delivered outside of the cardiac refractory period. This will be considered an AE if invasive intervention is taken. In the absence of invasive intervention, this will only be considered an AE if there is failure to capture the permanently programmed output with a minimum 2:1 safety margin. Sudden and significant increase in the pacing threshold value (elevated threshold compared to previous measured value) at which 2:1 safety margin can no longer be achieved.

Failure to sense or undersensing – Intermittent or complete loss of sensing or failure to detect intended intrinsic cardiac signals (atrial or ventricular) during non-refractory periods at programmed sensitivity settings. This will be considered an AE if invasive intervention is taken. In the absence of invasive intervention, this will only be considered an AE if the loss of sensing is not due to a medical reason and cannot be resolved with reprogramming.

Hematoma – A localized collection of extravasated blood, usually clotted, in an organ, space, or tissue. A hematoma is not considered a protocol defined AE unless it is a major hematoma related to the implant procedure. See major hematoma.

High pacing threshold – High lead pacing threshold resulting in invasive intervention. In absence of invasive intervention, at follow-up, lead threshold that has increased two fold from the chronic threshold value, and is unable to achieve a 2:1 safety margin.

IS-1 – the international standard whereby leads and generators from different manufacturers are assured a basic fit [Reference ISO 5841-3:2013]

Lead conductor fracture – A mechanical break within the lead conductor (includes connectors, coils and / or electrodes) observed visually, electrically, or radiographically.

Lead dislodgment – Radiographic, electrical, or electrocardiographic evidence of electrode displacement from the original implant site or electrode displacement that adversely affects pacing, and / or lead performance.

Lead insulation breach or insulation break – A disruption or break in lead insulation observed visually, electrically, or radiographically.

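### After a Plexa lead is replaced, lead measurements and the chronic-threshold reference stay on the removed lead's clock

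*Combined protocol and SAP*

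**What the plan says.** Section 3.2.6 (System Revisions) covers a Plexa lead replaced by another Plexa lead on a US market released generator from the sponsor: "the subject may continue participation in the registry based on the original implant date and visit schedule". Section 4.2 states that "The required follow-up visit dates are based on Plexa lead implant date" without saying which lead is meant after a replacement. Section 3.2.6 settles that in favour of the original one.

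For secondary endpoints 2 and 3 (pacing threshold, sensing, pacing impedance and shock impedance), section 2.4.3 says the measurements "will be summarized by scheduled visit through the 5 years of registry follow-up". Nothing separates or flags values from a replacement lead.

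Appendix A says "Chronic threshold is defined as the pacing threshold determined at the subject's 3 month follow-up visit". If that visit is missed, the first later value is used. The definition of high pacing threshold has two branches. One is "High lead pacing threshold resulting in invasive intervention", which needs no reference value. The other, without invasive intervention, is a "lead threshold that has increased two fold from the chronic threshold value, and is unable to achieve a 2:1 safety margin". Neither entry resets the reference for a new lead.

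One rule does follow the lead: the 30-day exclusions in section 9.3.1 run again from a lead revision procedure.

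**The concern.** The registry's stated purpose is long-term lead safety and reliability, with acute and chronic lead parameters evaluated. Section 1.4.1 itself notes that thresholds are often elevated after implantation, so the age of the lead matters for what is tabulated. A reader of the month-36 row will take it as the behaviour of three-year-old leads, and under the stated rules some of those leads may be months old.

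The threshold reference raises a different problem. A twofold rise is meant to describe change in one lead. After a later replacement the ratio has the new lead in the numerator and the removed lead in the denominator, so an event can be suggested or missed for reasons unrelated to the new lead. With one of the non-invasive responses listed in section 9.3.1, such an event can enter the primary endpoint.

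**Working it through.** **Lead age at a visit.** After replacement at month r, the lead seen at scheduled visit v has age v − r but is tabulated at v. Visits fall at 3, 6, 12, ..., 60 months. For replacement just after the month-30 visit:

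| Visit (months) | 36 | 42 | 48 | 54 | 60 |
|---|---|---|---|---|---|
| Age of lead in place (months) | 6 | 12 | 18 | 24 | 30 |

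All five later rows carry the wrong age. At six-monthly spacing, usually no more than one of them holds a value from a lead under 3 months old.

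This includes subjects who have already had a primary event. They may stay in after replacement, and their later values enter the same tables.

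**Effect on a tabulated mean.** Let f be the share of values at a visit from replacement leads and d their mean difference from original leads. The shift is f × d. The documents give neither. Assume f = 1% to 5% (7.5 to 37.5 of 750 subjects) and d = 0.35 V, one standard deviation of the GALAXY threshold (0.64 ± 0.35 V, section 1.3.1).

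- f = 1%: 0.01 × 0.35 = 0.0035 V, or 0.5% of 0.64 V.
- f = 5%: 0.05 × 0.35 = 0.0175 V, or 2.7% of 0.64 V.

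Means hardly move. Section 2.4.1 also allows minimums and maximums, and a single early value can set one of those.

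**Threshold reference.** Let c1 be the removed lead's 3-month value, c2 the new lead's own chronic value, and x a later reading. The plan asks whether x ≥ 2·c1. A lead-specific rule asks whether x ≥ 2·c2. The answers differ whenever x lies between 2·c1 and 2·c2. For illustration, take GALAXY mean ± 1 SD: 0.64 − 0.35 = 0.29 V and 0.64 + 0.35 = 0.99 V.

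- c1 = 0.29, c2 = 0.99: the limit is 0.58 V, so the new lead meets the twofold condition at its own stable value.
- c1 = 0.99, c2 = 0.29: the limit is 1.98 V, so the new lead must rise 1.98 / 0.29 = 6.8-fold.

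This is only one of two conditions. The 2:1 safety margin must also be unattainable, and the documents give no output figure from which to judge how often both would hold.

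**Primary endpoint, as a check.** The plan's sample size reproduces. With an exact binomial test, 92.5% against 95.0% and one-sided alpha 0.025, n = 750 is the smallest size with at least 80% power (at least 708 AE-free, alpha 0.0247, power 80.1%). Also 750 / 0.9^5 = 1270.1, rounded up to 1271. For replacement at 2.5 years, take a constant hazard h with exp(−5h) = 0.95, so h = −ln(0.95)/5 = 0.01026 per year. The subject's AE-free probability over two leads is exp(−2.5h) × exp(−2.5h) = 0.9747 × 0.9747 = 0.950, the same as for one lead over 5 years.

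**The case against.** The case for leaving the text alone is strong on size. Secondary endpoints 2 and 3 carry no hypothesis test. Values measured at a revision go on their own form.

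The threshold problem needs several things at once: replacement after the 3-month visit, no invasive intervention, loss of the 2:1 margin (which does not involve the old lead), and a response listed in section 9.3.1. Raising the output alone does not count. A lead replaced before the 3-month visit supplies its own value, though at a younger age. A subject replaced for a related, non-excluded event is already a primary failure. Appendix A's entry for failure to capture offers a parallel route that compares with the previous measured value, and thresholds are recorded at revision. The events committee also adjudicates category and relatedness.

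All of this stands, and it makes the point minor. It does not remove it, because no passage resets the reference or separates the values.

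A reader might go further and infer that the 5-year AE-free rate is overstated. Section 2.4.3 says "only subjects who achieve 5 years of follow-up or have experienced an adverse event prior to 5 years will be included", and section 9.2 says an event not adjudicated as related "will not have that individual event contribute to or be included in the evaluation of primary safety endpoint". A subject whose lead was replaced without a primary event can therefore count as AE-free although neither lead was in place for 5 years. Section 2.3 also counts evaluable leads where section 9.2 counts subjects. The documents do not support the inference. The endpoint is per subject from implant through 5 years, events on the new lead still count, and two leads at 2.5 years each make up the same 5 lead-years. With a constant hazard the difference is zero. With a hazard highest early, a new lead adds risk. Only a hazard rising with lead age would favour the device, and the documents do not state one.

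**Conclusion.** The point holds for two stated rules: the by-visit tabulation of secondary endpoints 2 and 3, and the chronic-threshold reference in the high-threshold definition without invasive intervention. Both assign the wrong lead age or the wrong lead after a replacement. The effect is small, and the endpoints affected are mainly descriptive. The replacement rate is not given, and GALAXY's 5.01% cannot stand in for it because it counts subjects with lead-related adverse events, not replacements. The shift of 0.0035 to 0.0175 V in a mean threshold rests on the assumed 1% to 5% share and the assumed 0.35 V difference. The primary test and the sample size are unaffected.

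**What to change.** Keep the subject's visit schedule as it is, and make two wording changes.

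1. In sections 2.4.1 and 2.4.3, restrict the main tables for secondary endpoints 2 and 3 to the original lead. Show post-replacement values in a separate table by age of the lead in place.
2. In Appendix A, define the chronic threshold as the value at 3 months from the implant date of the lead in place, or the first available value after that. On six-monthly visits that value will arrive at a lead age of 3 to about 9 months (3 + 6).

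No new data are needed. Section 3.2.6 already collects the revision date, the new lead's serial number and its electrical values, and section 4.2 provides a form for revision lead values. The cost is slightly fewer late-visit values in the main table.

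The Kaplan-Meier analysis should not be censored at replacement. That would leave the exact binomial test unchanged and would discard later events on replacement Plexa leads.
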